### **Reflexive LDL-C**

The endpoints involving LDL-C will use a reflexive LDL-C approach. When both calculated and beta-quantified LDL-C are available, calculated LDL-C will be used unless triglycerides are greater than 400 mg/dL or calculated LDL-C is less than 40 mg/dL. When only calculated LDL-C or beta-quantified LDL-C is available but not both, the available one will be used.

## **2.2 Analysis sets**

The following populations will be used for data analyses and/or presentation.

### **Intent-to-treat (ITT) population**

The ITT Population will include all subjects who entered into the study. Treatment classification will be based on the allocated treatment.

### **Modified intent-to-treat (mITT) population**

The mITT Population will include all subjects who receive at least one dose of study drug and have both the ORION-3 baseline and the Day 210 follow-up LDL-C (reflexive) assessment. Treatment classification will be based on the allocated treatment. This will be the primary population for analysis of the primary and secondary endpoints.

### **Safety (SAF) population**

The Safety Population will include all subjects who received at least one dose of study drug. Treatment classification will be based on the actual treatment received. This will be the primary population for the safety analyses.

[REDACTED]

[REDACTED]

#### **2.2.1 Subgroup of interest**

No subgroup analyses will be performed.

## **2.3 Patient disposition, demographics and other baseline characteristics**

### **2.3.1 Patient disposition**

Subject disposition will be summarized for the ITT population as follows:

- The number of subjects who were randomized for ORION-1 broken down by eligibility and consent status, who had a gap period, and who were treated will be summarized. The days from last dose in ORION-1 to first dose of study drug in ORION-3 will also be summarized.
- The number of subjects who consented and the number of subjects who were treated will be summarized by group and overall.
- The number of subjects in each analysis population will be summarized by group and overall.
- The number of subjects who completed the study or who discontinued early along with reasons for early discontinuation will be summarized by group and overall.
- The duration on study (number of days from the first date of study drug administration to the date of last recorded visit/contact date in the database) will be summarized by group and overall.
- Protocol deviations and violations of subject restrictions will be summarized by group and overall.

Select tables for Group 2 will be broken down by transition group (Transition 1 (staged) and Transition 2 (concurrent)).

Completers are defined as a subject who completes the Day 1440 visit.

### **2.3.2 Demographics and other baseline characteristics**

Subject demographics and background characteristics including age, sex, weight, height, BMI, race, ethnicity, country (country of participation), baseline eGFR and re-evaluation of child-bearing potential will be summarized using the ITT population. The following categorizations of quantitative variables will be performed:

- Age into  $\geq 18 - < 65$  and  $\geq 65$
- Age into  $\geq 18 - < 50$ ,  $\geq 50 - < 65$ ,  $\geq 65 - < 75$ ,  $\geq 75$
- Baseline eGFR into  $\geq 15 - < 30$ ,  $\geq 30 - < 60$ ,  $\geq 60 - < 90$ ,  $\geq 90$

Age collected in ORION-1 will be used but if the difference between consent date in ORION-3 and ORION-1 is greater than 365 days for a subject then 1 year will be added to the age for this subject.

Medical history (targeted and other medical history) will be summarized using the safety population. Other medical history will be coded into Medical Dictionary for Regulatory

Activities (MedDRA) terminology using the most recent MedDRA version before database lock (DBL), and will be summarized by primary system organ class and preferred term.

Summaries will be presented overall and by group (Group 1 and Group 2). Select tables for Group 2 will be broken down by transition group (Transition 1 (staged) and Transition 2 (concurrent)).

## **2.4 Treatments (study treatment, rescue medication, concomitant therapies, compliance)**

### **2.4.1 Study treatment / compliance**

Study drug administration will be summarized for inclisiran and evolocumab separately, overall and by visit. For inclisiran, the summary will include number of doses, actual dose for each injection, injection volume received, location for each injection, and occurrence of any medication errors. For subjects in Group 2 (switching arm), inclisiran administration after transitioning to inclisiran will be summarized by transition groups.

Duration of exposure to inclisiran in ORION-3 and cumulative exposure to inclisiran from ORION-1 through ORION-3 will be summarized. Duration of exposure to inclisiran will be calculated as: minimum of (Date of last dose of inclisiran – Date of first dose of inclisiran + 180) and (Date of last known visit/contact – Date of first dose of inclisiran). Patient years exposure (ORION-3 and cumulative) to inclisiran will also be summarized, which is calculated as (sum of duration of exposure to inclisiran)/365.25.

For evolocumab, the number and percent of subjects who have evolocumab administrations will be summarized for each planned time point of injection. Number of injections and number of missed injections will also be summarized.

Summaries will be presented for the safety population by treatment group (Group 1 and Group 2). Select tables for Group 2 will be broken down by transition group (Transition 1 (staged) and Transition 2 (concurrent)).

### **2.4.2 Prior and concomitant therapies**

Prior medications, baseline (Day 1 of ORION-3) concomitant medications, new or changed concomitant medications, and all prior and concomitant medications combined will be summarized by 3rd level Anatomical Therapeutic Chemical (ATC) classification and preferred name. Medications will be coded using the World Health Organization (WHO) drug dictionary.

Prior lipid modifying therapies (LMT), baseline (Day 1 of ORION-3) concomitant LMTs, new or changed concomitant LMTs, and all prior and concomitant LMTs combined will be

summarized by preferred name with dose and frequency. LMTs are medications with 3rd level ATC classification being either C10A (lipid modifying agents, plain) or C10B (Lipid modifying agents, combinations) according to the coding by the WHO drug dictionary. LMTs will be grouped into statins and other LMT. Statins will be further grouped by intensity (low, moderate, high) according to American College of Cardiology/American Heart Association (ACC/AHA) classification of statin intensity and based on the specific statin drug name, dose, and frequency recorded in the data.

Prior medication/LMT is defined as the medication stopped before Day 1 of ORION-3. Concomitant medication/LMT at Baseline (Day 1 of ORION-3), is defined as any medication onset before or on Day 1 (Day 1 of ORION-3) and either still ongoing or stopped on Day 1 (Day 1 of ORION-3) or later. Any medications with start date after study Day 1 (Day 1 of ORION-3) are considered as new or changed concomitant medications/LMT.

Summaries will be presented by group (Group 1 and Group 2). Select tables for Group 2 will be broken down by transition group (Transition 1 (staged) and Transition 2 (concurrent)). Analyses will be performed on the safety population.

## **2.5 Analysis supporting primary objective(s)**

The primary objective of this study is to evaluate the effect of inclisiran treatment on LDL-C levels at Day 210 compared to Baseline of ORION-1 in Group 1 (inclisiran only arm).

### **2.5.1 Primary endpoint(s)**

The primary efficacy endpoint is the percentage change from Baseline of ORION-1 in LDL-C at Day 210 in this study (Group 1; inclisiran only arm).

Summary statistics (n, mean, standard deviation (SD), median, first and third quartiles, minimum and maximum) for the percentage change in LDL-C and 95% confidence interval for the mean will be provided. One sample t-test will also be utilized to assess if the mean percent change from baseline to Day 210 is 0 or not. P-value (two-sided test) will be provided.

Analyses will be performed on the ITT and mITT populations.

### **2.5.2 Handling of missing values**

Missing data will not be imputed. Subjects missing any required data for computing the endpoint will be excluded from the analysis.

## **2.6 Analysis supporting secondary objectives**

The secondary efficacy objective of this study is to evaluate the effect of inclisiran on the following for Group 1 (inclisiran only arm):

- LDL-C levels over time
- PCSK9 levels over time
- Other lipids, lipoproteins, and apolipoproteins over time

- Individual responsiveness to inclisiran
- Proportion of subjects achieving target levels prespecified in global lipid guidelines
- Proportion of subjects with at least 50% LDL-C reduction from Baseline of ORION-1 over time

### **2.6.1 Secondary endpoint(s)**

The secondary efficacy endpoints of this study are:

- Observed value, absolute change and percentage change from Baseline of ORION-1 in LDL-C over time in this study
- Observed value, absolute change and percentage change from Baseline of ORION-1 in PCSK9 levels over time in this study
- Change and percentage change in LDL-C at Day 210 compared to Day 870 of ORION-3
- Observed value, absolute change and percentage change from Baseline of ORION-1 in other lipids, lipoproteins, and apolipoproteins, over time in this study
- Individual responsiveness to inclisiran defined as the proportion of subjects reaching on treatment LDL-C levels of <25 mg/dL, <50 mg/dL, <70 mg/dL, and <100 mg/dL over time and at any time point
- Proportion of subjects achieving global lipid targets for their level of ASCVD over time and at any time point
- Proportion of subjects with  $\geq 50\%$  LDL-C reduction from Baseline of ORION-1 over time and at any time point

The global lipid target is LDL-C level of < 70 mg/dL for ASCVD subjects and LDL-C level of < 100 mg/dL for ASCVD risk equivalent subjects.

Summary statistics (n, mean, standard deviation (SD), median, first and third quartiles, minimum and maximum) along with 95% confidence intervals for the mean will be provided for the continuous endpoints. The categorical variables will be summarized using the number and percentage of subjects who achieve each response level. 95% confidence intervals for the proportions will be provided.

Analyses will be performed on the ITT and mITT populations (Group 1; inclisiran only arm).

### **2.6.2 Handling of missing values**

Missing data will not be imputed. Subjects missing any required data for computing an endpoint will be excluded from the analysis.

## **2.7 Safety analyses**

All safety evaluations will be performed for the following groups unless otherwise specified:

- Subjects on evolocumab from the switching arm (Group 2) for the period between Day 1 (Day 1 of ORION-3) and Day 360.
- Subjects from the inclisiran only arm (Group 1), for the period from Day 1 (Day 1 of ORION-3) until EOS.

█ [REDACTED]

█ [REDACTED]

█ [REDACTED]

All the safety analyses will be performed on the safety population unless otherwise specified. Safety analyses are based on observed values. Any missing safety data including laboratory data will not be imputed.

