1.3 Study Rationale

1.3.1 Study Rationale

The overall safety data from inclisiran in nonclinical studies and clinical data from the Phase I ALN-PCSSC-001 study, the ALN-PCS02-001 study (ALN-PCS02 2014), and multiple PCSK9 antibody studies demonstrated that potent lowering of PCSK9 is well tolerated in human subjects and support the dose and dosing schedule proposed in this Phase II extension study. A switching arm has been added to this long-term extension to evaluate safety, tolerability and patient reported outcomes (PRO) compared to an active comparator (evolocumab) and [REDACTED]

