5.5 Blinding

Not applicable, this is an open-label study.

6 SCHEDULE and Sequence of Procedures

The Schedule of Events/Assessments ([Table 6-1](#) and [Table 6-2](#)) summarizes the study assessments by time point.

This study consists of three study periods:

- Observation Period: Consent/Study Entry until first dose on Day 1 (ORION-3)
- Treatment Period: Day 1 (ORION-3) to Day 360
 - Group 1 (inclisiran only arm)
 - Group 2 (evolocumab treatment; switching arm)
- Follow-up Treatment Period: Day 360 to EOS
 - all subjects on inclisiran

The expected duration of the subjects' involvement in the study will be approximately 4 years, which includes consent, study drug administration, and follow-up through the EOS visit (final visit which occurs 90 days following the final administration of study drug, or at least 30 days following the final administration of study drug if the study ends early or if the subject discontinues the study early).

At each visit, LDL-C levels, AEs, SAEs, concomitant medications, vital signs, and safety laboratory assessments will be collected.

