### **End of Study (EOS)**

EOS visit will occur at Day 1440, 90 days after the final administration of study drug (at Day 1350). However, if the study ends early or if the subject discontinues the study, the EOS visit should occur at least 30 days following the final administration of study drug.

Efficacy assessments will measure the effects of inclisiran on levels of LDL-C, lipids and lipoproteins including total cholesterol (TC), triglycerides, high-density lipoprotein cholesterol (HDL-C), non-HDL-C, very low-density lipoprotein cholesterol (VLDL-C), apolipoprotein A1 (Apo-A1), apolipoprotein B (Apo-B), lipoprotein(a) (Lp(a)), C-reactive protein (CRP), and proprotein convertase subtilisin/kexin type 9 (PCSK9).

At each visit, adverse events (AE), serious adverse events (SAE), concomitant medications, and safety laboratory assessments will be collected.

A Data Monitoring Committee (DMC) will review on a regular schedule the safety data. A recommendation may be taken to stop the study at any of these reviews.

Subjects enrolled into this extension study will receive study drug for approximately 4 years or

- until the investigator's recommendation of discontinuation,
- until the sponsor's recommendation of discontinuation,
- until the subject's decision to discontinue for any reason,
- until an administrative decision is made to end the study

[figure not shown]
If subjects, who have completed EOS visit (90 days after last dose administration), wish to continue treatment with inclisiran (and none of the above listed decisions or recommendations to discontinue the trial are in place) they will be given the opportunity to enroll into ORION-8 (open-label extension trial).

The protocol described the conduct of an interim analysis of lipids and PCSK9 upon completion of Day 210 for subjects in Group 1 (inclisiran only arm). Although there was a review of data upon completion of Day 210 for subjects in Group 1, no formal interim analysis report was generated. An interim analysis was conducted to evaluate Group 1 safety and tolerability data after all Group 1 subjects completed 24 months of treatment with inclisiran.

A schematic diagram of the study design is presented in [Figure 1-1](#).

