## 2 Statistical methods

### 2.1 Data analysis general information

All analyses will be performed by Novartis or a designated clinical research organization (CRO). The most recent version of SAS available in the statistical programming environment of Novartis or the designated CRO will be used for the analysis.

All study-collected data will be summarized by treatment group using descriptive statistics, graphs, and/or raw data listings. Categorical variables will be summarized using counts and percentages. Percentages are based on the number of subjects in the analysis set for whom there are non-missing data, unless otherwise specified. Continuous variables, including changes from Baseline of ORION-1 or ORION-3, will be summarized using descriptive statistics (n (number of non-missing observations), mean, standard deviation (SD), median, first and third quartiles, minimum and maximum). The precise definitions of the baselines are given in [Table 2-1](#).

Absolute change and percent change from baseline will be calculated as follows:

- Absolute Change from baseline to Day X = Value at Day X – Baseline value.
- Percent Change from baseline to Day X = (Absolute Change/Baseline value)\*100%.

Analyses for the final CSR will be conducted after all participants complete the EOS visit or discontinued early. [REDACTED]

Information regarding DMC analysis will be provided in the DMC charter and a separate DMC SAP/TFL shells.

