### 2.7.1 Adverse events (AEs)

Adverse events will be summarized for every group specified above in [Section 2.7](#).

The most recent version of MedDRA before DBL will be used for coding AEs. An AE (classified as preferred term) will be counted as a treatment emergent AE (TEAE) if the AE started after the first treatment in ORION-3 or the AE was present prior to the first treatment in ORION-3 but increased in severity after initiation of study drug in ORION-3. Only TEAEs will be summarized in the tables, but the subject data listings will include all AEs.

The following summary tables will be presented:

- Overall Summary of TEAEs
- TEAEs by primary system organ class (SOC) and preferred term (PT)
- TEAEs by PT
- TEAEs by primary SOC, PT, and severity
- TEAEs related to study drug by primary SOC, PT
- Treatment Emergent Serious AEs (TESAEs) by primary SOC and PT
- TESAEs by PT
- TESAEs related to study drug by primary SOC, PT
- TEAEs leading to withdrawal of study treatment by primary SOC and PT
- TEAEs with a fatal outcome by primary SOC and PT
- TEAEs at the injection site by primary SOC and PT
- Clinically relevant TEAEs at the injection site (listed in [Appendix 5.3](#)) by PT

- TEAEs at the injection site by primary SOC, PT and severity
- Prespecified signs and symptoms at the injection site

If more than one event occurred with the same preferred term for the same subject, the subject will be counted only once for that preferred term, using the most severe occurrence for the summary by severity. For select tables, exposure-adjusted incidence rate (EAIR) will be calculated for subjects from the inclisiran only arm (Group 1), for the period from Day 1 (Day 1 of ORION-3) until EOS, [REDACTED]

EAIR is defined as the total number of subjects with the event / total exposure (years) \* 100%, where total exposure = sum of duration from start date of inclisiran injection in ORION-3 to the onset date of the event (the last visit/contact date will be used for the patients without the event).

TEAEs at the injection site include all TEAEs identified as being an injection site reaction on AE Case Report Form (CRF) or with “injection site reactions” as the high level term (HLT).

The following additional adverse events will be assessed (Refer to [Appendix 5.2](#) for the detailed definitions):

1. Hepatic events
  2. Renal events
  3. Hypersensitivity
  4. Neurological events and Neurocognitive disorders
  5. Ophthalmological events
- [REDACTED]

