### **2.7.3 Laboratory data**

Summaries for laboratory values will include observed value, changes and percent changes from ORION-3 baseline at each time point.

A shift analysis using the normal range (except for eGFR and HbA1c) will be done which counts the number of subjects with a low, normal or high value at ORION-3 baseline and a low, normal or high value post baseline.

The following ranges will be used for eGFR and HbA1c:

- For eGFR, the categories will be Severe =  $< 30 \text{ mL/min/1.73m}^2$ ; Moderate =  $\geq 30$  to  $< 60 \text{ mL/min/1.73m}^2$ ; Mild =  $\geq 60$  to  $< 90 \text{ mL/min/1.73m}^2$ ; and Normal =  $\geq 90 \text{ mL/min/1.73m}^2$ .
- For HbA1c, the categories will be  $< 5.7\%$ ,  $\geq 5.7\%$  to  $< 6.5\%$ , and  $\geq 6.5\%$ .

The shift table for the fasting glucose will require the lab sample to be taken while fasting. Samples taken while the subject was not fasting will not be analyzed.

The number and percentage of subjects with potentially clinically significant (PCS) laboratory values and clinically significant (CS) laboratory values (refer to [Appendix 5.4](#) for the criteria) will be summarized by treatment group. HbA1c criteria is explicitly stated in [Appendix 5.4](#). All other PCS and CS criteria are met when both of the following occur:

- Worst post-baseline value meets the thresholds listed in [Appendix 5.4](#)
- Baseline value does not meet the thresholds in [Appendix 5.4](#)

Separate listings of all subjects with PCS and CS laboratory values will be presented. Subjects will appear once per lab parameter but may appear under multiple lab parameters. The worst post-baseline value will be utilized in the analyses.

The number and percentage of subjects satisfying Hy's Law will also be tabulated based on the following lab findings:

- Any elevated post-baseline aminotransferases defined as:
  - $\text{ALT} > 3 \times \text{ULN}$  or
  - $\text{AST} > 3 \times \text{ULN}$
- Elevated post-baseline serum total bilirubin (TBL)  $> 2 \times \text{ULN}$  and serum alkaline phosphatase (ALP) levels  $< 2 \times \text{ULN}$

Subjects must meet all of the criteria listed above at the same time point and have normal lab parameters (ALT, AST, TBL) at baseline to be considered a Hy's Law case. A second summary will be presented that includes subjects who meet all of the criteria listed above at the same time point without regard to the baseline lab parameter results.

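### The visible safety columns cover about one year for evolocumab and about four for Group 1, and the EAIR definition cannot give an evolocumab rate: match the first-year window and define that rate

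*SAP*

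**What the plan says.** SAP 2.7 sets the default groups for all safety evaluations. Two are visible: "Subjects on evolocumab from the switching arm (Group 2) for the period between Day 1 (Day 1 of ORION-3) and Day 360" and "Subjects from the inclisiran only arm (Group 1), for the period from Day 1 (Day 1 of ORION-3) until EOS". Three further entries are blacked out. SAP 1.1 (End of Study) puts the final visit at Day 1440.

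SAP 2.7.1 applies these groups to adverse events and counts a subject once per preferred term. SAP 2.1 fixes the measure: "Categorical variables will be summarized using counts and percentages". For selected tables an EAIR is added for Group 1 over Day 1 to EOS; the rest of that sentence is redacted. The definition itself is fully visible: "total exposure = sum of duration from start date of inclisiran injection in ORION-3 to the onset date of the event", with last contact used for subjects who have no event.

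SAP 2.7.3 reports the percentage of subjects with potentially clinically significant (PCS) or clinically significant (CS) laboratory values: "The worst post-baseline value will be utilized in the analyses".

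Protocol 1.3.1 says the switching arm was added to "evaluate safety, tolerability and patient reported outcomes (PRO) compared to an active comparator (evolocumab"). Protocol section 6 already names a matching first-year period for both groups: "Treatment Period: Day 1 (ORION-3) to Day 360".

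**The concern.** A percentage of subjects with at least one event grows with follow-up. Set side by side, a 360-day column and a 1440-day column differ even if the two drugs carry the same risk. A worst post-baseline laboratory value behaves the same way, because more tests give more chances of an extreme result. The usual remedy is a rate per patient-time, but the visible rate counts time only from the inclisiran injection. Group 2 first receives inclisiran at the Day 360 visit, so its whole evolocumab year falls before that clock starts. This holds whatever the redacted end of the EAIR sentence says.

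At stake is how the safety tables are read. A reader looking for the comparison with evolocumab described in protocol 1.3.1 could take a window artefact for a drug difference.

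**Working it through.** The plan states no figure on this point, so there is none to reproduce.

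**Window lengths (SAP 2.7 and 1.1).** Evolocumab: 360/365.25 = 0.99 years. Group 1: 1440/365.25 = 3.94 years. The ratio is 4.0.

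**Scheduled post-baseline tests (protocol 7.1.6; no assumption needed).**
- ALT/AST, evolocumab: Days 30, 90, 180, 270 and 360 = 5.
- ALT/AST, Group 1: limited chemistry on Days 30, 90, 180, 270, 390, 450, 540, 570, 630, 810, 870, 990, 1170, 1260 and 1350 (15), plus full chemistry on Days 360, 720, 1080 and EOS (4) = 19.
- HbA1c: Day 270 for evolocumab (1), against Days 270, 540, 810, 1080, 1350 and EOS for Group 1 (6).

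**Effect of window length on percentages.** The documents give no event rates, so I assume a constant hazard r, equal in both columns. Without dropout, the proportion with an event is 1 − exp(−rT). With an assumed dropout hazard d = 0.10 per year it is r/(r+d) × [1 − exp(−(r+d)T)].

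| Assumed r per year | Evolocumab, 360 days | Group 1, 1440 days | Ratio | Ratio with dropout |
|---|---|---|---|---|
| 0.05 | 4.8% | 17.9% | 3.7 | 3.2 |
| 0.10 | 9.4% | 32.6% | 3.5 | 3.0 |
| 0.30 | 25.6% | 69.4% | 2.7 | 2.4 |
| 1.0 | 62.7% | 98.1% | 1.6 | 1.5 |

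The direction can mislead too. With 0.10 per year on evolocumab and half that, 0.05, in Group 1, the table gives 9.4% against 17.9%: the group with the lower hazard shows the higher percentage.

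**What the Group 1 EAIR already repairs.** Under a constant hazard the EAIR estimates 100r per 100 patient-years. Beside the evolocumab percentage this gives 5 against 4.8%, 10 against 9.4%, 30 against 25.6%, and 100 against 62.7%. Since evolocumab follow-up is about one year, the two nearly agree for uncommon events and part company for common ones.

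**Precision of an evolocumab rate.** Assume the 382 enrolled subjects (protocol, Amendment 5 rationale) split as ORION-1 was randomised, 127 placebo of 501 (protocol 1.2.2): 382 × 127/501 = 96.8, about 97. At an assumed 0.10 per year, subjects with an event = 97 × 0.0939 = 9.1, and person-time = 9.1/0.10 = 91 years. The exact Poisson 95% interval for 9 events in 91 years is 4.5 to 18.8 per 100 patient-years. With 80 subjects it is 4.6 to 21.0; with 120, 4.9 to 17.5.

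**The case against.** The strongest reply has four parts.

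1. **Redaction.** A Group 1 Day 1-360 column could be among the three blacked-out groups. This stands. A reader might infer that the matched column is missing, but the documents do not support that, and it is not claimed here.

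2. **No visible comparison is broken.** The visible safety objective (protocol 2.2) concerns Group 1 only, and no between-group safety test is visible. Day 1 to EOS is the window that objective needs, and Day 1-360 is essentially all the evolocumab follow-up the design offers. This also stands: protocol 1.3.1 is a rationale, not a visible objective. A reader might infer a biased safety test, but none is visibly planned.

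3. **The EAIR already helps.** For uncommon events in the selected tables it largely does, as shown above. A reader might infer that every safety table is distorted three- to fourfold; that goes too far. By-visit summaries through Day 360 are unaffected as well.

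4. **An evolocumab rate needs care.** Protocol 4.4.2 asks subjects who meet its laboratory stopping criteria to complete the remaining visits without study drug. Someone stopped during the evolocumab year may never start inclisiran, and without a cap could contribute time well past Day 360. In Transition 2 the last evolocumab dose follows inclisiran at the same visit (protocol 6.6.1), so the definition must say where later events go. Both points stand and are built into the fix.

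It is also tempting to say that a cut at Day 360 puts days after inclisiran into the evolocumab column, since that visit has a window of ±7 days. That follows only if Day 360 means the calendar day; the SAP can equally be read as meaning the visit.

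**Conclusion.** The point holds as a minor one about presentation and labelling. Established from the visible text: a fourfold difference in window length, 5 against 19 scheduled ALT/AST tests, 1 against 6 HbA1c tests, and an EAIR denominator that contains no evolocumab time. The ratios of about 1.6 to 3.7 (1.5 to 3.2 with dropout) rest on assumed equal constant hazards and assumed event and dropout rates. The effect matters mainly in tables without an EAIR, for common events, and in the PCS/CS laboratory table, to which the default windows of SAP 2.7 apply.

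Matching the windows removes only the window artefact. A reader might infer that the matched columns would then be a fair test of inclisiran against evolocumab. They would not: protocol 3.6.1 calls the study nonrandomised, and Group 1 had inclisiran in ORION-1 where Group 2 had placebo. The primary endpoint is unaffected.

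**What to change.** In SAP 2.7, 2.7.1 and 2.7.3:

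1. Confirm that a redacted safety group already gives Group 1 for Day 1-360. If not, add that column beside evolocumab in the main TEAE tables (overall, SOC/PT, serious, injection site) and the PCS/CS table.
2. Define an evolocumab rate per 100 patient-years with a 95% interval. Count time from the first evolocumab dose to the earliest of event, first inclisiran dose, last contact, or a cap at the Day 360 visit. For subjects who receive no inclisiran, set the cap at study Day 360 plus the 7-day visit window. Show it beside a Group 1 rate over the same first-year window.
3. State that events after the Day 360 visit in Transition 2 are assigned to the inclisiran period, although a final evolocumab dose was given at that visit.
4. State that the comparison is descriptive and nonrandomised, that Group 1 had prior inclisiran in ORION-1, and that Day 1-360 and Day 1-EOS percentages should not be compared directly.
5. Wording only: express the EAIR per 100 patient-years instead of multiplying by 100%.

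The cost is one added column and one added rate, with no new data. If the matched column already exists, only the rate and the text remain. The rate will be imprecise (about 4.5 to 18.8 per 100 patient-years under the assumptions above), which is why it needs its interval.
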